## **2. SOLUTION AND RESEARCH**

### **2.1. PROPOSED SOLUTION AND APPLICABILITY SCENARIOS**

This proposal seeks to build "school communities" based on Public Schools (PS), aimed at promoting MH in children and their families and detecting early MH problems in students, providing them with initial support and subsequent coordinated referral to treatment.

To achieve this, it is proposed to construct a participatory multicomponent intervention aimed at promoting the MH of children attending basic education in. The components of this grant are: 1) a Child Mental Health (CMH) Literacy program for PS teachers, which will be built in a participatory manner with them and other key actors; and, 2) the articulation of the local network of care in child and adolescent mental health, including several levels of complexity (community, primary care and specialized care) and, which occupies the strategy ECO-BARRIO SOLIDARIO with adaptations according to the new socio-sanitary context. Given the nature of a pilot project that, in the first instance, seeks to evaluate the feasibility of this intervention, its implementation is proposed in two neighborhoods of Valparaíso, with a random selection of 8 PS with primary education in each of

these neighborhoods, after the implementation of the program, the initial effectiveness of the literacy component in CMH will be evaluated with the teachers.

The process of participatory construction of the Literacy program in CMH will be developed during the first 12 months of the project, for which we will work with representatives of the academic body of these EEPs (teachers, parateachers, directors and others), parents, students, directors of the Local Education Service (SLEP) of Valparaíso and representatives of the ECO-Barrio network.

Through working groups and individual interviews with key actors, a survey of objectives, methodology and contents of the CMH Literacy program will be made. Due to the health situation derived from the COVID-19 Pandemic and the current development of Information and Communication Technologies (ICTs), an asynchronous and asynchronous online program is proposed, based on recorded video educational capsules and discussion groups with CMH specialists respectively. There will be an evaluation at the beginning and at the end of the course, to measure acquired knowledge and level of satisfaction in terms of methodology and content, among others, in addition to evaluating the application process in a qualitative way. The course will be free and certified by the Faculty of Medicine of the University of Valparaíso. The certification will be automatic for those who complete all the requirements on the online platform, which will be accessible from computers or mobile phones. The total duration of the course should be between 3 to 4 months.

Parallel to the construction of the CMH Literacy program for teachers, the "ECO BARRIO SOLIDARIO" strategy will be implemented in one of the neighborhood with modifications according to the new health and contextual scenario, which will be called "ECO-Barrio Network". The strategy of the ECO-Barrio Network is feasible to replicate given that in Primary Health Care (PHC) there are the Joint Commissions of Health-Education (COMSE), which aim to link CESFAM with the Educational Establishments that converge in a territory, to develop strategies for prevention, participation and health promotion in educational communities. Particularly in Valparaíso, since 2020 and in the face of the socio-health crisis due to COVID-19, it is developing a COMSE 2.0 strategy, whose objectives are: 1) to re-activate the COMSE meetings with the participation of Mental Health Managers of each school, psychosocial duo of the PHC health team and in charge of participation and promotion of CESFAM. 2) Develop a socio-educational process for COMSE participants to improve the referral and follow-up of cases from the educational community to PHC, in addition to the development of prevention and promotion strategies in MH and 3) Develop a containment, prevention and promotion device in MH for the educational communities of the educational establishments of the polygon associated with each CESFAM. These new objectives of COMSE 2.0 are aligned with the ECO-Barrio Network strategy and with this project. The contribution of the ECO-Barrio Network strategy will be to systematically convene potential participants of the COMSE, including all relevant participants in the CMH of that neighborhood (Health from primary care with the CESFAM and CECOF that correspond plus specialized care with the Outpatient Unit of Child and Adolescent Psychiatry of the Psychiatric Hospital of Salvador (HDS), SENAME in its different programs and others such as Life Skills (HPV). In addition, from the articulation with the Secondary level of Mental Health and the link with the chair of Child Psychiatry of the University of Valparaíso, the ECO-neighborhood Network will be able to organize and provide training, generate the case monitoring system on an online platform and evaluate the implementation process in the two selected neighborhoods which will serve as an input for a potential replication to other territories of Valparaíso.

This project promotes and strengthens the co-construction of responses and articulated strategies for children, making visible the community role as the central axis of action. This multimodal intervention can help to address the serious increase in CMH problems derived from the COVID-19 pandemic and the social crisis, but it is also considered a useful model to function in a stable way throughout Chile, since it considers interventions to increase the knowledge and resolutivity of the faculty in CMH, a component not addressed in other instances of research or management known in our country.

The relevance and feasibility of scaling up to the rest of the country is ensured with the participatory process of local key actors, in addition to the participation of SLEP, Health and I. Municipality of Valparaíso. This proposal is aligned with the community approach contemplated in the National Plan for MH and Psychiatry 2017-2025 and seeks to respond to the increase in MH problems in the child adolescent population and reduce social inequalities that remain in our country despite macroeconomic growth.

## **2.2. RESEARCH QUESTION**

Is it feasible and effective a multi-component intervention, built in a participatory manner and with a territorial perspective, to improve the level of mental health of children in public educational establishments, identifying and treating those who need it?

## **2.3. RESEARCH HYPOTHESES OR ASSUMPTIONS**

1. Teachers who participate in a Child Mental Health Literacy program are able to significantly improve their knowledge regarding the identification of these problems and the delivery of first aids.
2. The establishments that participate in this training program significantly improve the detection rate of children with mental health problems.
3. The relevance of the diagnosis made by teachers when referring children with mental health problems to the corresponding CESFAM is greater than 80%.
4. The health-education networks where an intervention is carried out to articulate the referral of girls and girls with mental health problems, reduce the waiting time that goes between the referral and the first health care.

## **2.4. OBJECTIVES**

### **2.4.1. GENERAL OBJECTIVE**

Evaluate the effectiveness and feasibility of a multicomponent intervention, built in a participatory manner and with a territorial approach, to improve the level of mental health of children in public educational establishments, identifying and treating those in need in a timely manner.

### **2.4.2. SPECIFIC OBJECTIVES**

1. Build in a participatory way the contents of a literacy program in Child Mental Health (CMH) with teachers of Public Educational Establishments (PS) and key actors, from the commune of Valparaíso.
2. Implement the strategy of articulation in a network of CMH (ECO-Neighborhood Network) between schools, Primary and Secondary Health Care, Municipality, collaborating agencies of SENAME and other relevant programs in 2 territories of the commune of Valparaíso.
3. To evaluate whether the Child Mental Health Literacy program, aimed at teachers in public educational establishments, manages to significantly improve their knowledge in this regard.
4. To assess whether teachers participating in the CMH Literacy program significantly improve the detection rate of these problems among their pupils.
5. To evaluate whether the relevance of the research for referral from educational establishments to the corresponding CESFAM is greater than 80%.
6. To evaluate whether the health-education articulation strategy (ECO-Barrio Network) significantly improves waiting times between referral and the first care received by a child with a possible mental health problem.
7. Evaluate indicators of feasibility of the multicomponent intervention, which are useful for a future escalation (interest of teachers to participate, retention in the intervention, degree of satisfaction of all participants, facilitators and perceived barriers).

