To calculate the necessary sample size, the following parameters were considered: a prevalence of mental disorders of 27.8% and an identification rate of 30% of these cases (9 cases per 100 children, per year). This indicator (which corresponds to scenario 2 and specific objective 4) was taken as one of the most important achievements and reflects the impact of the intervention as a whole. To accept the fulfillment of our hypothesis, it will be necessary to double the identification rate to 60% of cases (18 cases per 100 children, per year). In this way, it is a comparison of proportions, where:  $p_1 = 0.3$ ,  $p_2 = 0.6$ , a confidence level of 95% for a unilateral test and a power level of 90%, 56 children are needed in each group. However, it is expected to work with a much larger sample: if it is considered that in each establishment there are 30 children per grade and only one course per level (from 1st to 8th grade). This would lead us to a potential sample of 240 children per establishment, which implies 480 in intervention facilities and 480 in control facilities.

Development of fieldwork. The development of the fieldwork has three fundamental stages: 1) Implementation of the ECO-Neighborhood Network strategy in the 1 selected neighborhood, (months 1

to 18), 2) the participatory construction of the components of the intervention (months 12 months); and 3) pilot-level evaluation of this intervention (months 12-24).

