1. The first stage (months 1 to 18) The component of the intervention aimed at articulating educational establishments with mental health devices (CESFAM teams and secondary level in Health), within specific territories, whose purpose is to expedite the care of these children, will be implemented. It is the so-called ECO-Barrio Network, for whose implementation a working committee will be formed for each sector where the study is implemented, with representatives of all these institutions, in addition to the I. Municipality of Valparaíso. This committee will begin by analyzing the barriers that hinder the referral of children with mental health problems, and then establish a specific work plan in each sector (with objectives, activities, goals and deadlines). The activities of this plan will be implemented in parallel to the intervention with the teachers, in the second part (months 7 to 18, so that the times are concordant). In addition, follow-up meetings of referrals will be held with 1 representative of each CESFAM with ECO BARRIO coordinator and the 4 schools intervened, in a modality that includes virtuous meetings with bimonthly frequency. Finally, this stage of work will include at least one weekly meeting of the FONIS team with advisors and coordinators of RED ECO and Literacy Program.
2. The second stage (months 1 to 12) consists of the participatory construction of the contents of a training program on children's mental health, aimed at teachers of public educational establishments, which will use e-learning (with asynchronous and synchronous activities) and whose contents will be based on their experience with respect to of the problems they distinguish, the way they identify them, the obstacles they have in handling them, and the opportunities for support they can provide (including the relationship with their parents). To collect the experience of the teachers, a working group will be created in each establishment participating in the project, which will collect the experience of the teachers on this subject. In addition, in-depth individual interviews will be conducted. Then, one or two teachers from each group (from each establishment) will be invited to participate in a team with psychologists and psychiatrists from the project, to design the course together. The contents and methods of the course will be made by the research team, under the supervision of the team that includes teachers, technical advisors and audiovisual equipment.

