3. The third part (months 12 to 24) consists of carrying out a pilot test taking 4 educational establishments located in two different territories of the commune of Valparaíso, in which the intervention will be carried out, and its results will be compared with 4 other equivalent educational establishments, from those same territories, which serve as control. Pre- and post-intervention assessments will be carried out, using a children's mental health knowledge survey, while referrals from facilities to the corresponding CESFAM will be recorded. Results will be compared between intervention and control results. Information is also collected to assess the participation of teachers in the intervention (feasibility analysis).

At the end of the intervention in the establishments that were the object of it, the quantitative indicators and results that were collected will be synthesized, and a qualitative analysis will be carried out (DEXPLIS design), based on discussion groups that involve the interested parties (teachers, mental health professionals and managers of both sectors). in which the results and achievements will be analyzed, barriers and facilitators of the process will be established, all of which will allow to complete the evaluation in a participatory way and to improve the components of the intervention, based on the empirical experience carried out.

After the end of the intervention, the intervention will also be carried out in its two components (teachers and health-education network) in the 4 establishments that served as control. In this way, an ethical requirement of not depriving the rest of the participants of a beneficial intervention is met. (Months 18 to 24)

Indicators, instruments and analysis procedures. For the detailed description of this point, the effectiveness analysis and the feasibility analysis of the pilot intervention are separated.

1) Evaluation of the effectiveness of the intervention. The effectiveness evaluation is based on comparing the following indicators between intervention and control establishments.

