### 3.3. WORK PLAN

Specific Objective	Activity	Months																							
		1	2	3	4	5	6	7	8	9	10	11	12	13	14	15	16	17	18	19	20	21	22	23	24
1-Build in a participatory way the contents of a Literacy program in CMH	1-Presentation of the Ethics Committee Project	x																							
	2- Random selection of the 4 PS		x																						
	3-Contact and invitation to working meetings of key informants of the territories and PS		x	x																					
	4- Establish work teams in each selected PS			x																					
	6- Participatory design of the literacy program			x	x	x	x																		
2. Implement the ECO-Barrio network strategy	1- Contact with key agents of the CMH network	x																							
	2-Form a committee in each sector with the representatives of the institutions of the intersectoral ecosystem in CMH	x																							
	3- Develop a participatory work plan with objectives, goals, activities, deadlines and managers.		x	x	x																				
	4-Bimonthly work and follow-up meetings.			x	x	x	x	x	x	x	x	x	x	x	x	x	x	x	x						
3. Assess whether the literacy program significantly improves knowledge in CMH	1- Recruitment of teachers to participate in the literacy intervention.			x	x	x	x																		
	2- Development of knowledge instrument in CMH			x																					
	3-Test of application of the instrument in PS of non-intervened sectors.				x																				
	4-Semantic adaptation of the instrument.					x																			
	5-Implementation of online literacy course (G1 and G2)							x	x	x	x	x	x	x	x	x	x	x	x						
	6 Evaluation of teachers intervened with instrument (pre and post intervention)							x					x							x					
4- Evaluate if the detection rate of CMH problems is significantly improved	1-Random selection of 2 PS similar to those selected in a neighborhood where the intervention has not been implemented				x																				
	2- Determine the detection rate in schools that received the literacy program compared to control schools												x										x		
5.Evaluate whether the relevance of referral to	1- Determine how many of the referred children enter Mental Health treatment (regardless of the device or level of complexity)						x	x	x	x	x	x	x	x	x	x	x	x	x						

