###### **4.1.2. IMPLEMENTATION OF THE EXPECTED PRODUCT(S)**

The direct beneficiaries will be PS teachers from the commune of Valparaíso who receive basic education students and who voluntarily agree to participate in the child mental health literacy program. To this end, an e-learning platform will be developed with audiovisual resources for training in CMH, asynchronously, in addition to contemplating some synchronous meetings to resolve doubts with the participants of the training.

Additionally, training activities and facilitation of intersectoral coordination will be programmed for health, education, SENAME and other relevant actors, in order to support the process of identifying students who require mental health care in an opportune and pertinent manner, through the eco-neighborhood network that will be implemented in 2 sectors of Valparaíso. those that will be carried out online, given the current global health context, and taking advantage of the familiarity that has been given with these means that facilitate the meetings and reduce the expenditure of resources for their participants.

In relation to the e-learning platform, the project will remain as an input for CORMUVAL and the ECO-Barrio Network, so that they can continue using it in their activities.

Finally, the development of a critical nucleus and associativity of the University of Valparaíso with specialized groups is expected, which promotes more research in this area and constitutes updated and complementary information to what is currently available, in addition to contributing to the technological development of science solutions applied to public health in the area of child mental health. These expert groups have been described throughout the project.

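### The detection difference is credited to the literacy course in some places and to the whole intervention in another; on the staging text it is a package effect, and the controls' access to the network is unsettled

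*Combined protocol and SAP*

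**What the plan says.** Three places attach the detection outcome to the teacher course:

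- Hypothesis 2 (section 2.3): "The establishments that participate in this training program significantly improve the detection rate of children with mental health problems".
- Objective 4 (section 2.4.2): "To assess whether teachers participating in the CMH Literacy program significantly improve the detection rate of these problems among their pupils".
- Work plan, objective 4, activity 2 (section 3.3): "Determine the detection rate in schools that received the literacy program compared to control schools".

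One place attaches it to the package. The sample-size paragraph of section 3.1 ties the indicator to specific objective 4 by number, uses it to size the trial, and says it "was taken as one of the most important achievements and reflects the impact of the intervention as a whole".

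On delivery, section 3.1 (first stage) says of the network work plan: "The activities of this plan will be implemented in parallel to the intervention with the teachers". The referral follow-up meetings there involve the four intervened schools. The third stage says that, once the intervention has ended, "the intervention will also be carried out in its two components (teachers and health-education network) in the 4 establishments that served as control".

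**The concern.** One outcome carries two meanings, and it is the outcome on which the trial was sized. If the network acts in the intervention schools and not in the controls, a higher detection rate could come from the course, from the network, or from both together. The report would nonetheless be entitled, under objective 4, to say that trained teachers detect more.

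The network could plausibly move this outcome directly. Its committees begin by examining what hinders referral (section 3.1, first stage). Section 4.1.2 gives it training and coordination "in order to support the process of identifying students who require mental health care". The detection rate is calculated from a school register of children whom teachers indicate as needing care, and the same register serves to coordinate referral (section 3.1, effectiveness indicator b). If referral becomes easier, teachers may register more children even if their knowledge has not changed.

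At stake is what the pilot may conclude about its main quantitative outcome, and which component a later reader believes produced the effect.

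**Working it through.** **The plan's own figures.** Section 3.1 gives p1 = 0.30, p2 = 0.60, 95% confidence, 90% power and 56 children per group. With pooled variance under the null and no continuity correction,

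n = [z(alpha) × sqrt(2 × 0.45 × 0.55) + 1.2816 × sqrt(0.30 × 0.70 + 0.60 × 0.40)]² / 0.30²

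- Two-sided, z = 1.96: (1.379 + 0.860)² / 0.09 = 55.7, so 56. This matches the plan.
- One-sided, as the text states, z = 1.645: (1.157 + 0.860)² / 0.09 = 45.2, so 46.

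The mismatch on sidedness is a separate matter. What counts here is that the calculation contains one contrast, 0.60 − 0.30 = 0.30, and no term for either component.

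**What that contrast measures if controls have neither component.** Write R(both), R(network) and R(neither) for the identification rates under course plus network, network alone, and neither. Then

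R(both) − R(neither) = [R(both) − R(network)] + [R(network) − R(neither)]

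The left side is what the trial observes, planned at 30 points. The first bracket is what the course adds. The second is the network alone. No arm is defined as network alone or course alone, and no analysis is planned that separates the two, so neither bracket can be estimated. The documents give no value for R(network), so no size can be put on the course's share.

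**Do controls have neither component?** The passages disagree.

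- Pointing to neither: section 3.1, first stage (follow-up meetings with the four intervened schools) and third stage (both components given to controls only afterwards); section 3.3, objective 4, activity 1 (controls drawn from a neighborhood where the intervention has not been implemented).
- Pointing to a shared network: the Summary (the literacy intervention is what is given to four of eight schools); section 2.1 (the literacy component is what will be evaluated with teachers); section 3.1, first stage (one committee per sector); section 3.1, third stage (controls come from the same territories); section 3.1, indicator b (the register, with its referral coordination, is kept in control schools too).
- Unclear on reach: section 2.1 and the fieldwork paragraph of section 3.1 place the network in one neighborhood, while objective 2 and section 4.1.2 say two.

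**What each answer implies.**

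1. Controls have no network: the contrast is R(both) − R(neither), a package effect.
2. Controls have part of it: the control rate reflects an unmeasured dose of network. The contrast still mixes the course with the remaining network difference, so the course effect is not identified.
3. The network runs equally in both arms: the contrast is R(both) − R(network), the course added to the network. Only here does objective 4's wording fit.

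**The mirror case.** Hypothesis 4 and objective 6 credit shorter waiting times to the network alone. Under answers 1 and 2 the arm comparison gives a package effect on waiting time. Under answer 3 the arms do not differ in the network, so the comparison does not test the claim.

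**The case against.** The strongest reply is that control exposure is not settled, so the objective cannot be called wrong. The Summary and section 2.1 read as a literacy-only contrast, the network is organised by sector, controls are in the same territories, and control schools have a register that allows coordinated referral. The training in section 4.1.2 is delivered across sectors, so it may reach both arms. On that reading objective 4 is roughly right. This stands as far as it goes: a reader might infer that the documents establish that controls go without both components, and they do not. But the reading needs equal coverage of both arms, and the staging text in section 3.1 says otherwise.

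A second reply is that objective 4 merely names the group being compared, while the general objective, the design statement and the sample-size text all speak of a multicomponent intervention. That is possible, but hypothesis 2 says that schools in the training program improve detection, which reads as attribution.

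Two stronger readings are also tempting. One is to put a percentage on how far the course effect would be overstated. That needs a network-only detection rate, which the documents do not give. The other is that the course is a stand-alone product, so misattribution would mislead its adopters and the larger study. Section 4.1.2 leaves the platform to the municipal corporation and to the network itself, and the Summary says the larger study would evaluate the multicomponent intervention, for which a package effect is the relevant quantity.

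**Conclusion.** The concern holds in a conditional form. The inconsistency between hypothesis 2, objective 4 and the work plan on one side and the sample-size paragraph on the other is plain in the text. On the delivery described in the first and third stages of section 3.1, the comparison is course plus network against neither and does not support a course-specific conclusion on detection. Partial sharing of the network leads to the same conclusion. Only equal delivery of the network in both arms would support the claim, and then as the course added to the network.

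The whole planned 30-point difference is affected in meaning, but its division between components cannot be sized from the documents. The sample size does not change. Evaluating a package is a legitimate choice for a pilot and agrees with the general objective; the defect lies in the claim attached to it. The point should be settled before results are analysed, because it determines what may be concluded from the outcome used to size the trial.

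**What to change.** First, reconcile the Summary, section 2.1, section 3.1 (fieldwork paragraph, first and third stages, indicator b) and section 3.3 on one question: which parts of the network, if any, do control schools have during the controlled period, and in which neighborhoods?

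Then match the claims to the answer.

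- If controls do not have the network, or have it only in part: reword hypothesis 2, objective 4 and work-plan objective 4, activity 2 as the effect of the multicomponent intervention as delivered versus control on the school detection rate, and drop the course-only attribution. Reword hypothesis 4 and objective 6 as a package effect on waiting time.
- If the network runs equally in both arms: say so, define the detection contrast as the course added to the network, and align the sample-size paragraph with it. State that the network's effect on waiting time is not tested by the arm comparison.

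This costs wording only, with no new schools, arms or data. The downside is that the sponsor may give up component-specific claims for detection and waiting time.
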